#### 7.3.1.2 *Deep Cognitive and Behavioral Assessments During Treatment*

Participants will be asked to perform a 10-minute “Well-being” assessment that includes open-ended questions about major domains of health. Examples include how they are, concerns, physical symptoms, emotional symptoms, social interactions and perceived support, medications and missed pills, energy and activity, sleep, a 1-5-minute story describing something that happened to them during the week and tests of short-term memory, working memory and attention.

## 7.4 Remote Visits/Telehealth

Some study visits and/or procedures may be conducted remotely in the following circumstances:

- Telehealth visits do not present an increased risk to the participant.
- All necessary data for the trial can be collected.
- Procedures do not include research related imaging, lab samples, and/or pathology which should be conducted in person.

Note: The method of telehealth should be documented in the participants' charts.

## 8 ADVERSE EVENTS

### 8.1 Definitions

#### 8.1.1 Adverse events

21 CFR 312.32, ICH GCP, and OHRP define an adverse event as any untoward medical occurrence whether or not considered treatment-related. This definition extends to the worsening of any preexisting condition or symptom. All adverse events experienced during trial participation should be documented in the subject's research chart and corresponding eCRF.

Laboratory abnormalities should not be listed as adverse events unless deemed clinically significant by the investigator or qualified designee. An abnormal test result or findings should not be recorded as an adverse event unless the following conditions are met:

- Associated with clinical symptoms; and/or
- Requires intervention (medical, surgical, or additional diagnostic testing); and/or
- Results in a change in study drug dosing; and/or
- Deemed by the investigator or qualified designee to be an adverse event.

While disease progression should be noted in the subject's research chart, it should not be reported as an adverse event.

#### 8.1.2 Serious Adverse Events

A serious adverse event is defined as any untoward event that is:

- Fatal;
- Life-threatening;
- Results in persistent or significant disability/incapacity;
- Medically significant;
- Causes a congenital abnormality or birth defect;
- Requires or prolongs inpatient hospitalization.

Investigator judgment must be used to assess an event as medically significant. The event may not be life-threatening or cause disability but may jeopardize the subject and require intervention to prevent the other SAE outcomes.

The following situations should not be reported as an SAE:

- Hospital admission not associated with a precipitating AE such as:
  - Treatment for a preexisting condition not associated with a new AE or the worsening of a preexisting condition;
  - Admission for social or administrative reasons;
  - Optional admission or elective surgery;
  - Observation;
  - Preplanned treatments or surgical procedures as noted at baseline;
  - Admission for the administration of blood products.

## 8.2 Adverse Event Reporting

The investigator and qualified designees are responsible for the detection, documentation, reporting, and follow-up of all adverse events experienced by subjects during trial participation. AEs and SAEs will be recorded from consent until 30 days after the last dose of study medication or until new cancer therapy is started. The following information will be required for each adverse event:

- Event severity as graded by the CTCAE v.5;
- The causality assessment to study medication per the below definitions;
- Expectedness
- Event duration;
- Any action taken to treat or manage the event;
- Event outcome.

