## 1.2 Schema

#### 1.4 Schedule of Events

Activity	Screening	Preparatory Session (Baseline)	Ketamine Sessions 			Integration Session	Follow-Up 		
			1	2	3		14 Days	30 Days	90 Days
Visit						0	(±3)	(±7)	(±7)
(Window in days)	-60	0							
Informed Consent	X								
Demographics	X								
Medical History	X								
Eligibility Criteria	X								
Registration 	X								
Clinical and Laboratory Assessments									
Vital Signs 	X		X 	X 	X 				
Physical Exam	X								
ECOG Score	X								
ECG	X		ACI						
Adverse event collection 	X	X	X	X	X	X	X		
Concomitant medications	X	X	X	X	X	X	X		
Complete Metabolic Panel	X								
Urine Drug Screen	X								
Pregnancy Test 	X								
Study Intervention									
Evaluation and Screening 			X	X	X				

Activity	Screening	Preparatory Session (Baseline)	Ketamine Sessions 			Integration Session	Follow-Up 		
			1	2	3		14 Days	30 Days	90 Days
Visit						0	(±3)	(±7)	(±7)
(Window in days)	-60	0							
Ketamine Administration 			X	X	X				
Psychotherapy		X	X	X	X	X			
Assessments									
EDS 	X	X	X	X	X		X	X	X
QIDS-SR-16 		X	X	X	X		X	X	X
C-SSRS Baseline/Screening 	X								
C-SSRS Since Last Visit 		X	X	X	X	X	X		
MEQ-30 			X	X	X				
NADA 			X	X	X				
DADDS 		X	X	X	X		X	X	X
FACIT-Sp 		X					X	X	X
Storyline Integrative Assessment 		X					X	X	X

---

 Ketamine will be given during three sessions, 2 to 7 days apart. Questionnaires, with the exception of the MEQ, may be completed up to 1 day prior to the ketamine session.

 Follow-up will be based on time since completion of the integration session.

 To register eligible patients on study, complete a Clinical Trials Office Subject Registration Form and submit to [[contact]](mailto:[contact]).

 Laboratory assessments should be completed within 28 days of enrollment.

 Vital signs include systolic/diastolic blood pressure, heart rate, respiration rate, pulse oximetry and weight.

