 Cardiovascular measures during KAP session (blood pressure, O2 sat, heart rate) will be completed within ten minutes prior to session and at 40 min and 2 hours post-administration. Vitals will be reviewed by an on-site MD with ACLS certification. A crash cart and code response team will be available.

 Adverse events and conmeds will be recorded at the time of the session. Subjects may also be contacted by study staff after the session to assess for any additional adverse events or conmed changes.

 Pregnancy test (serum or urine) must be obtained at screening and  $\leq$  8 days prior to ketamine administration for all women of childbearing potential and as clinically indicated while on trial.

 Evaluation and screening to include the items listed in Section 6.1.2.

 Ketamine will be administered according to Section 6.1.3.

 Existential Distress Scale (EDS). See Appendix 2.

 Quick Inventory of Depressive Symptomatology (QIDS-SR-16). See Appendix 3.

 Columbia-Suicide Severity Rating Scale Baseline/Screening (C-SSRS). See Appendix 4.

 Columbia-Suicide Severity Rating Scale since Last Visit (C-SSRS). To be completed at any time during study participation if a subject is rated as of moderate or high risk on the Baseline/Screening C-SSRS. See Appendix 5.

 Mystical Experiences Questionnaire (MEQ-30) should be completed after ketamine administration. See Appendix 8.

 Nondual Awareness Dimensional Assessment. See Appendix 7.

 Death and Dying Distress Scale. See Appendix 9.

 The Functional Assessment of Chronic Illness Therapy. See Appendix 6.

 See Section 3.3.

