## 6.6 Concomitant Medications and Therapies

All supportive measures consistent with optimal subject care may be given throughout the study.

All administered concomitant medications (including herbal supplements) and non-medicinal therapies (including transfusions) used 28 days prior to registration, and until 30 days after the last dose of study therapy will be recorded in the subject's research chart and corresponding eCRF, if applicable.

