### **7.1.4 Concomitant Medications**

All medications currently being used by a study participant, regularly or as needed, must be reviewed and documented by the investigator or qualified designee. Specific attention should be given to medications with a protocol required washout as described in the exclusion criteria and any medication taken 28 days prior to ketamine. Refer to Section 6.5.1 for prohibited medications.

During protocol therapy, any medications taken by the patient or used to treat an adverse event will be documented in the subject's research chart and the corresponding eCRF. If a new anticancer therapy is initiated during study follow-up, the new therapy should also be recorded in the subject's research chart and corresponding eCRF...

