### **7.2.2 Adverse Events**

Adverse events experienced during trial participation will be collected per the Schedule of Events and Adverse Events Section. Each study participant will be questioned about the occurrence of adverse events in a non-leading manner.

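### Adverse events and concomitant medications must be recorded to 30 days after the last dose, but the Schedule of Events stops asking about them at the 14-day follow-up visit

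*Combined protocol and SAP*

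**What the plan says.** Section 8.2 fixes the recording period for adverse events: "AEs and SAEs will be recorded from consent until 30 days after the last dose of study medication or until new cancer therapy is started". Section 6.6 covers concomitant medications "until 30 days after the last dose of study therapy will be recorded" and gives no cut-off for new cancer therapy. Section 7.1.4 adds: "If a new anticancer therapy is initiated during study follow-up, the new therapy should also be recorded".

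In Section 1.4, the row "Adverse event collection" and the concomitant-medication row below it are marked at screening, the preparatory session, the three ketamine sessions, integration and the 14-day follow-up. Both are blank at the 30-day and 90-day follow-ups, although those visits take place and collect questionnaires. Footnote 2 sets the clock for these visits: "Follow-up will be based on time since completion of the integration session". Footnote 7 says: "Subjects may also be contacted by study staff after the session to assess for any additional adverse events or conmed changes".

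Section 7.2.2 requires active questioning ("Each study participant will be questioned about the occurrence of adverse events in a non-leading manner") and refers the reader to both the Schedule and the adverse event section for how events are collected.

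**The concern.** The duty to record runs to 30 days after the last dose, while the last planned question comes at a visit 14 days (±3) after integration. Unless integration is held long after the last dose, the remaining days rely on spontaneous report, chart review or a contact that staff may choose not to make. Capture of that kind is likely to vary between subjects.

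Safety and tolerability is the first secondary objective (Section 2.2.1). It is reported as adverse event and serious adverse event frequencies over all treated subjects (Section 9.4.1), in a trial that Section 8.4 classes as high risk. With 12 subjects, one subject whose only event is missed changes an incidence by 1/12, about 8 percentage points. Section 7.1.4 also expects new anticancer therapy in follow-up to be recorded, yet no medication question is scheduled after the 14-day visit to find it.

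**Working it through.** The plan gives no figure for this gap, so there is none to reproduce. The check is calendar arithmetic, followed by a search for any text that would close the gap.

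**Inputs**
- End of recording window: day 30 after the last dose (Sections 8.2 and 6.6). For adverse events only, the start of new cancer therapy can also end it.
- Last scheduled query: 14 days ± 3 after integration (Section 1.4).
- Next planned visit: 30 days ± 7 after integration (Section 1.4).
- d = days from last dose to integration. The readable text does not give this and the schema figure is not shown, so d is an assumption and a range is used.

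**Column check.** The Existential Distress Scale row in the same table is blank at integration and marked at all three follow-ups. The columns therefore line up, and the blank 30-day and 90-day cells are not an artefact of text extraction.

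**Unqueried days, no new cancer therapy**
- Last query in post-dose days: d + 14 ± 3 = d + 11 to d + 17.
- Days left: 30 − (d + 17) to 30 − (d + 11) = 13 − d to 19 − d, floored at 0.

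**Coverage if the 30-day visit is used**
- Visit in post-dose days: d + 30 ± 7 = d + 23 to d + 37.
- Largest shortfall from day 30: max(0, 7 − d).

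| d (assumed) | Last query, post-dose day | Unqueried days to day 30 | 30-day visit, post-dose day | Largest shortfall of that visit |
|---|---|---|---|---|
| 0 | 11–17 | 13–19 | 23–37 | 7 |
| 1 | 12–18 | 12–18 | 24–38 | 6 |
| 7 | 18–24 | 6–12 | 30–44 | 0 |
| 14 | 25–31 | 0–5 | 37–51 | 0 |
| 19 | 30–36 | 0 | 42–56 | 0 |

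At nominal visit timing the gap is 16 − d days and closes at d = 16. Across the whole visit window it closes only at d = 19.

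**Effect of new cancer therapy.** Suppose it starts on post-dose day t and Section 8.2 means the earlier of the two dates. Unqueried adverse event days are then max(0, min(30, t) − (d + 17)) to max(0, min(30, t) − (d + 11)). For t = 20, chosen only as an illustration:
- d = 1: 20 − 18 = 2 to 20 − 12 = 8 days.
- d = 7: 0 to 20 − 18 = 2 days.
- d = 14: none.

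The concomitant-medication gap does not change with t, because Section 6.6 has no such cut-off.

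**Does other text close the gap?**
- Section 7.2.2 points to both the Schedule and the adverse event section, which stop at different times, so it does not settle the matter.
- Footnote 7 contact is optional and undated.
- Section 8.2 makes the investigator responsible for detection but schedules no contact.
- Section 8.2.4 follows known events to stabilization or resolution; it does not find new ones.
- The FACIT-Sp at Day 30 (Appendix 6) asks about nausea, pain and treatment side effects, but no text sends those answers to the adverse event forms.

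The footnote 2 rule does not cause the problem. Counting from integration moves the 14-day visit later relative to the last dose, which narrows the gap.

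**The case against.** The strongest reply is that a recording window and a query schedule are different things. The plan can be read as active questioning to 14 days and passive capture afterwards, and both can be obeyed together. The Since Last Visit suicidality scale stops at the same visit, which fits a deliberate pattern, though no text says so. This is a single-centre trial (Section 5.5.2) that recruits from the investigators' own clinics (Section 5.5) and takes its source data from the medical record (Section 11.1). Admissions, deaths and new prescriptions can therefore reach the chart without a Schedule mark. Section 3.1 describes ketamine as having a short half-life, every dosing session is queried, and the safety analysis is descriptive with no threshold. The size of the gap also rests on an interval that cannot be seen, and it may be zero.

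Much of this stands as a limit on size. Serious events are less likely to be lost than mild late ones, no decision rule in the plan depends on the missing data, and the number of days is conditional on d. It does not remove the mismatch. Nothing states that late capture is meant to be passive, Section 7.2.2 asks for questioning, and Section 6.6 asks for all concomitant medications to day 30.

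A fair point on cost also stands. All Day 30 entries in the Schedule are questionnaires or the Storyline assessment, and Section 3.3.2 has app notifications prompting assessments. A staff question at Day 30 may therefore be a new contact, not only a new mark in a table.

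**Conclusion.** The concern holds. The plan requires recording to 30 days after the last dose but schedules no adverse event or concomitant-medication query after the 14-day follow-up. The blank cells are certain. The length of the gap is 13 − d to 19 − d days, floored at zero, and depends on the assumed interval d. For adverse events it is shorter if new cancer therapy starts first.

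The consequence is a risk of modest under-ascertainment in the tail of the safety window, probably mainly of mild late events. The dosing sessions, integration and the 14-day visit are all queried, and the primary endpoint is unaffected. The change is worth making because it is cheap and serves the first secondary objective.

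A lesser point is the wording of the window's end. Section 6.6 has no new-therapy cut-off and Section 8.2 has one, while Section 8.3.1, on pregnancy exposure, is alone in saying that the earlier date applies. The conclusion does not rest on this.

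**What to change.** 1. In Section 1.4, mark adverse event and concomitant-medication collection at the 30-day follow-up visit.
2. Add a footnote that this final query covers the period to 30 days after the last dose or, for adverse events, to the start of new cancer therapy if earlier. If the visit falls before post-dose day 30, a brief remote contact on or after that day completes the query. Section 7.4 already provides for this: "Some study visits and/or procedures may be conducted remotely in the following circumstances".
3. Reconcile Sections 1.4, 6.6 and 8.2 on the end of the window. State whether the Section 8.2 cut-off means the earlier date, as in Section 8.3.1, and whether it also applies to concomitant medications.
4. Leave the footnote 2 timing of the questionnaire visits as it is.

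The cost is two Schedule cells, one footnote, a few more data entries and a short staff contact at Day 30 if that visit is otherwise completed through the app. The extra remote contact can arise only if d is below 7, since the 30-day visit cannot fall before post-dose day 30 otherwise.

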### 5.1 Inclusion Criteria

1.  Subject aged  $\geq$  18 years.
2.  Subjects with non-operable GI cancers requiring multi-modal treatment (e.g. surgery +/- chemo +/-radiation) and have a high likelihood of recurrence and/or treatment failure in the opinion of the treating investigator.
3.  Screen positivity for existential distress on the EDS, defined as scoring  $\geq$  3 on any of the 10 component domains, or a total score  $\geq$  6
4.  ECOG Performance Status  $\leq$  2.
5.  Adequate hepatic function as defined as:
  - Total Bilirubin  $\leq$  1.5x institutional upper limit of normal (ULN) unless elevated bilirubin is related to Gilbert's Syndrome
  - AST(SGOT)/ALT(SGPT)  $\leq$  3  $\times$  institutional ULN
    - Subjects with liver metastases will be allowed to enroll with AST and ALT levels  $\leq$  5  $\times$  ULN.
6.  For subjects of childbearing potential: Negative pregnancy test or evidence of post-menopausal status. The post-menopausal status will be defined as having been amenorrheic for 12 months without an alternative medical cause. The following age-specific requirements apply:
  - Subjects  $<$  50 years of age:
    - Amenorrheic for  $\geq$  12 months following cessation of exogenous hormonal treatments; and
    - Luteinizing hormone and follicle-stimulating hormone levels in the post-menopausal range for the institution; or
    - Underwent surgical sterilization (bilateral oophorectomy or hysterectomy).
  - Subjects  $\geq$  50 years of age:
    - Amenorrheic for 12 months or more following cessation of all exogenous hormonal treatments; or
    - Had radiation-induced menopause with last menses  $>1$  year ago; or

- Had chemotherapy-induced menopause with last menses >1 year ago; or
- Underwent surgical sterilization (bilateral oophorectomy, bilateral salpingectomy, or hysterectomy).

7.  Subjects of childbearing potential and subjects with a sexual partner of childbearing potential must agree to use a highly effective method of contraception as described in Section 5.3.1.

8.  Subjects with a sexual partner of childbearing potential must agree to use a condom during intercourse for 24 hours post- ketamine dose.

9.  Agree to refrain from using any psychoactive drugs, including alcoholic beverages, ondansetron, cannabis, and non-routine PRN medications within 24 hours of each ketamine administration. Exceptions include daily use of caffeine, nicotine, and opioid pain medication (see Section 6.5.1).

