### 6.6.1 Prohibited Therapy

Medications or vaccinations specifically prohibited in the exclusion criteria are not allowed during the active treatment period. Patients are prohibited from receiving the following therapies during the treatment phase of this trial:

- Other investigational agents
- Herbal remedies known to potentially interfere with major organ function (e.g., hypericin)
- Monoamine oxidase inhibitors
- Sedatives – any opioid, benzodiazepine, sedative hypnotic, or alcohol
- Theophylline or Aminophylline
- Sympathomimetics (excluding albuterol) and Vasopressin

Patients will be advised to refrain from the following for 12 hours before ketamine:

- Cannabis
- Psychostimulants-includes methylphenidate, any amphetamines, modafinil, or armodafinil
- Non-routine PRN medications

On the day of ketamine administration, patients on opioids should not take any long-acting opioids within 12 hours prior to or 6 hours proceeding ketamine administration. Patients should consume approximately the same amount of caffeine-containing beverage (e.g., coffee, tea) that he/she consumes on a usual morning, before arriving at the research unit. If the subject does not routinely consume caffeinated beverages, he or she must agree not to do so on the day of ketamine administration. Patients should also not use nicotine for at least 2 hours before ketamine administration. .

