### **6.7.1 Criteria for the Discontinuation of Treatment**

Subjects may withdraw from treatment or the study overall at any time at their request, or they may be withdrawn at the discretion of the Investigator or Sponsor for safety, behavioral reasons, or the inability of the subject to comply with the protocol-required schedule of study visits or procedures. In addition to the drug-specific discontinuation criteria listed in section 6, the following will result in treatment discontinuation:

- Completion of treatment study visits outlined in the Schedule of Events
- The subject or legally authorized representative requests to discontinue the study treatment and/or study procedures;
- Clinical deterioration that, in the opinion of the investigator, increases the risk to the subject;
- Adverse events or intercurrent illness that in the opinion of the investigator warrants the subject's withdrawal from study treatment;
- Significant noncompliance with the protocol schedule or treatment administration in the opinion of the investigator;
- Pregnancy

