### 9.4 Secondary Endpoints

#### 9.4.1 The frequency of adverse events (AEs) and serious adverse events (SAEs) characterized by type, severity (as defined by the NIH CTCAE, version 5.0), seriousness, duration, and relationship to study treatment.

All subjects who receive any study treatment will be included in the final summaries and listings of safety data. The detailed information collected for each AE will include a description of the event, duration, severity, relatedness to study drugs, action taken, and clinical outcome. The severity of the AEs will be graded according to the CTCAE v5.0. The statistical analysis of the safety data will be descriptive and tabular.

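### Section 8.2 lets the start of a new cancer therapy end AE and SAE recording, although ketamine is not the cancer treatment and other sections set no such cut-off

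*Combined protocol and SAP*

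**What the plan says.** Section 8.2 gives the only start and stop points stated in words for safety recording: "AEs and SAEs will be recorded from consent until 30 days after the last dose of study medication or until new cancer therapy is started". It does not say whether the earlier or the later end point governs, and it does not restrict the second to the time after the last ketamine dose.

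On the population, inclusion criterion 2 (5.1) reads "Subjects with non-operable GI cancers requiring multi-modal treatment (e.g. surgery +/- chemo +/-radiation", and adds that patients must "have a high likelihood of recurrence and/or treatment failure in the opinion of the treating investigator".

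On cancer therapy during the trial, 6.6.1 introduces its list with "Patients are prohibited from receiving the following therapies during the treatment phase of this trial". The list bars other investigational agents and several drug classes, but not standard anticancer therapy. Section 6.7.1 lists what stops ketamine under the words "the following will result in treatment discontinuation"; starting a cancer regimen is not on that list. Section 7.1.4 adds: "If a new anticancer therapy is initiated during study follow-up, the new therapy should also be recorded".

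On collection and analysis, 8.1.1 says "All adverse events experienced during trial participation should be documented in the subject's research chart and corresponding eCRF", and 9.4.1 says "All subjects who receive any study treatment will be included in the final summaries and listings of safety data".

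**The concern.** Ending AE recording at the next cancer therapy is natural when the study drug is itself the cancer treatment, because the next regimen replaces it and confuses attribution. Here ketamine is given for existential distress. A new regimen neither replaces it nor ends exposure to it, so the cut-off stops observation for a reason unrelated to the study drug.

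At stake is secondary objective 2.2.1, the safety and tolerability of the intervention. A subject whose record was closed early still counts among the treated subjects in the summaries. An unobserved period then looks the same as a period without events, and the reported frequencies can only move downward.

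**Working it through.** The plan states no figure that depends on the recording window, so there is nothing to reproduce. The check is a comparison of sections, followed by window arithmetic.

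**1. Can a new regimen start while ketamine is still to be given?** Consent may come up to 60 days before the preparatory session (Schedule of Events). From then on, nothing in 6.6.1 bars a new standard regimen and nothing in 6.7.1 stops ketamine when one starts. It is therefore permitted before dose 1, between doses and in the 30-day tail. Section 7.1.4 expressly foresees it only in follow-up. Continuing an existing regimen would not trigger the clause, which refers to new therapy.

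**2. Which end point governs?** Section 8.2 is silent. Section 8.3.1 pairs the same two end points for pregnancy exposure and says that the one occurring first applies. That supports the earlier-event reading of 8.2.

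**3. What do the other sections require?**

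| Place | Rule | New-therapy cut-off? |
|---|---|---|
| 8.2, window sentence | Consent to 30 days after last dose, or new cancer therapy | Yes |
| 8.2, preceding sentence, and 8.1.1 | All AEs during trial participation | No |
| Schedule of Events, AE row | Screening through the 14-day follow-up, including each ketamine session | No |
| Schedule of Events, footnote 7 | AEs recorded at the session; later contact optional | No |
| 8.2.5 | All SAEs reported within one business day | No |
| 6.6 | Concomitant therapies recorded to 30 days after last dose | No |

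No section says which rule prevails. Section 7.2.2 points to both the Schedule of Events and the adverse event section, which disagree.

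The AE row does not cover the tail reliably. The 14-day visit (±3) falls 11 to 17 days after the integration session. The interval from session 3 to that session is not stated. Scheduled collection reaches 30 days after the last dose only if the interval is at least 30 − 17 = 13 days (latest visit) to 30 − 11 = 19 days (earliest visit). The 30-day and 90-day visits carry no AE mark.

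**4. Window arithmetic.** Three sessions, 2 to 7 days apart:
- First to last dose: 2 + 2 = 4 days to 7 + 7 = 14 days.
- Recording window from first dose without the cut-off: 4 + 30 = 34 to 14 + 30 = 44 days.
- New regimen d days after the last dose: 30 − d tail days lost, no doses lost.
- New regimen the day after session 1, read literally: 34 − 1 = 33 to 44 − 1 = 43 days lost, with two of three doses still to come.
- New regimen between consent and dose 1, read literally: no recorded time on ketamine.
- One subject of 12: 1/12 = 8.3% of the planned sample.

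**5. Illustration only.** The share q of subjects starting a new regimen in the window is not given. Expected number affected is 12q, and P(at least one) = 1 − (1 − q)^12.

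| Assumed q | Expected affected | P(at least one) |
|---|---|---|
| 10% | 1.2 | 0.72 |
| 25% | 3 | 0.97 |
| 50% | 6 | >0.99 |

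Take an AE with an assumed true rate of 10%, and the extreme case in which an affected subject contributes no record at all. With n fully recorded subjects, P(at least one event seen) = 1 − 0.9^n, and the one-sided 95% upper bound after zero events is 1 − 0.05^(1/n).

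| n | P(at least one seen) | Upper bound after zero events |
|---|---|---|
| 12 | 0.72 | 22% |
| 9 | 0.61 | 28% |
| 6 | 0.47 | 39% |

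With 12 kept as denominator, the expected reported frequency would be 10% × 9/12 = 7.5% or 10% × 6/12 = 5%. These figures show how the mechanism works and do not estimate what will happen.

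**The case against.** The strongest reply is that the protocol already requires collection at every point where ketamine is given. Staff working from the Schedule of Events and footnote 7 would record AEs at each session whatever the cancer treatment, and 8.1.1 asks for all AEs during participation. This stands: it turns a certain loss into a possible one. It does not remove the conflict, because 8.2 is where the window is defined and no order of precedence is given.

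A second reply is that the clause applies only after dosing. It sits beside the 30-day tail, and 8.3.1 covers the treatment period separately and speaks of subsequent anticancer therapy. That reading is available. Even so, the tail is shortened for a reason unrelated to ketamine, and follow-up differs between subjects.

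A reader might infer more than the documents support:
- *That events during ketamine exposure will be lost.* The competing rules mean only that they can be.
- *That the DSMC will see fewer SAEs.* Sections 8.2.5 and 8.4 require all SAEs to be reported and reviewed, without the cut-off, so this is not established.
- *That losses fall on the frailest, progressing patients.* A new regimen may be the next planned modality, and eligibility requires ECOG 2 or less. The documents do not describe who would change regimen.
- *That the plan expects new regimens between doses.* Section 7.1.4 speaks of follow-up only. The earlier periods are permitted, not predicted.
- *That 33 to 43 days of exposure disappear.* Those are recording days at the literal extreme, mostly post-dose tail after single injections of a drug that 3.1 describes as having a short half-life.

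**Conclusion.** The concern holds as an internal conflict with a definite direction of bias and an unknown size. As written, 8.2 allows a new cancer regimen to close the AE and SAE record in the 30-day tail and, read literally, before or between doses, while other sections require collection without that limit. Because every treated subject stays in the summaries, AE frequencies could be understated. Without a rate of new regimens, or knowledge of which rule sites will follow, the amount cannot be estimated.

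This rests on reading 8.2 as stopping at the earlier event, which 8.3.1 supports, and on new standard regimens being permitted, which 6.6.1 and 6.7.1 leave open. It should be fixed, but it is not critical: the endpoint is secondary, descriptive and tabular, and the primary feasibility endpoint does not use AE data.

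**What to change.** - In 8.2, delete the words that end recording at the start of new cancer therapy, so that every treated subject is recorded from consent to 30 days after the last ketamine dose.
- Align the matching clause in 8.3.1.
- Align the AE row of the Schedule of Events with the same window, so that a scheduled contact covers the end of the 30 days.
- Require the start date of any new anticancer therapy. Section 7.1.4 asks for the therapy to be recorded but names no date.
- In the safety listings, flag AEs with onset after that date.

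Limiting the clause to the period after the last dose would protect the dosing period but would leave the tail uneven between subjects, so deletion is preferable.

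The cost is a short amendment needing IRB approval, possibly one added contact, and some extra AEs attributable to cancer therapy. The causality categories in 8.2.2 already allow for events explained by other drugs or by the underlying disease.
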